Inclusion/Exclusion criteria (TI, EI, Subject). Exclude ACSS assessment and FACE-Q Satisfaction with Skin assessment if Randomization does not occur during this visit^b	X
Urine pregnancy test ^c	X

^a Includes blood pressure (systolic and diastolic) while subject is seated, pulse rate, and temperature.

^b ACSS assessment by TI and FACE-Q Satisfaction with Skin assessment by Subject are to be performed only at Randomization visit. Note: it is possible the subject will subsequently be deemed ineligible for the study once these assessments are performed at the Randomization visit.

^c For female subjects of childbearing potential; administered and confirmed negative. A female subject is not considered of childbearing potential if she has been postmenopausal for at least 1 year or does not have a uterus at the time of study entry.

Table 2-2 Treatment Group Procedures

^a Randomization must occur within 30 days of screening; screening visit and randomization visit can occur on the same day if subjects do not require washout. If screening and randomization visits occur on the same day, inclusion/exclusion criteria and urine pregnancy testing need not be repeated.

b The TI may perform a touch-up treatment, 30 days after initial treatment, if the TI determines that optimal correction was not achieved with initial treatment. If no touch-up treatment is performed, Day 30 visit becomes Month 1 visit.

c Study exit visit is at Month 6 for subjects not receiving repeat treatment. If repeat treatment is performed, Month 6 will be repeat treatment visit, and exit visit will be at Month 4 after repeat treatment.

^d For female subjects of childbearing potential; administered and confirmed negative prior to randomization/treatment. A female subject is not considered of childbearing potential if she has been postmenopausal for at least 1 year or does not have a uterus at the time of study entry.

e Randomization and initial treatment for the treatment group must occur on the same day.

On treatment days, vision assessments will be performed before treatment and approximately 30 minutes after treatment.

The treatment procedure is to be performed after all effectiveness assessments and 2D facial imaging.

h The 30-day daily safety e-diaries are to be completed following each treatment starting on the day of treatment and are considered complete if all days are completed until the Day 30/Month 1 visit.

Table 2-3 Control Group Procedures (No-Treatment Period)

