7.2 Treatment Modification

Retreatment Criteria

A subject may receive touch-up treatment if optimal correction has not been achieved at Day 30 in the opinion of the TI and is agreed upon by both subject and TI. The TI will have access to the EI-rated ACSS scores to assist in making the determination of whether optimal correction has been achieved. All treatment group subjects are eligible to receive repeat treatment at Month 6 if desired.

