5.3.2. Main Analytical Approach

The missing data in ACSS at Month 1 of CP will be imputed using the Multiple Imputation (MI) method for the mITT population as follows:

Step 1: The missing data will be imputed by cheek side and treatment group using the Fully Conditional Specification (FCS) method with seed = 820403 and nimpute = 30 based on the following model:

$$\text{Month 1 ACSS} = \beta_0 + \beta_1 \times \text{Age} + \beta_2 \times \text{Baseline ACSS}$$

Step 2: After imputation, the changes from baseline will be calculated, from which the responder status in ACSS at Month 1 of CP will be determined.

Step 3: Each complete dataset obtained from Steps 1 and 2 will be analyzed using SAS procedure FREQ

Step 4: The pooled results will be obtained using PROC MIANALYZE

The number and proportion of participants who achieved at least 1-point improvement from baseline at Month 1 of CP will be tabulated by treatment group. The aggregated responder rates by treatment group and the associated p-value and 95% CI estimated based on the normal approximation to assess the difference in the ACSS responder rate at Month 1 of CP between JUVÉDERM VOLITE XC and the no-treatment control will be presented. If the 2-sided p-value is less than 0.05, then the ACSS responder rate at Month 1 in JUVÉDERM VOLITE XC is statistically significantly different from that in the no-treatment control group during the control period. Furthermore, if the responder rate is greater for JUVÉDERM VOLITE XC than the no-treatment control group, then VOLITE will be considered superior to the no-treatment control group.

The detailed SAS codes are as follows:

```
proc mi data=adeff seed=820403 nimpute=30 out=mi;
  by trt01p cheek;
  class acss0 acss1;
  fcs logistic(/details);
  var age acss0 acss1;
run;
data lmi rmi; *separate imputed datasets by cheek side;
  set mi;
  if cheek='Left' then output lmi;
  if cheek='Right' then output rmi;
run;
data all; *obtain responder status variable;
  merge lmi rmi;
```

JUVÉDERM VOLITE™ XC

```
by _imputation_ subjid;
ldiff=lacss0-lacss1;
rdiff=racss0-racss1;
resp=0;
if ldiff >= 1 and rdiff>=1 then resp=1;
run;
ods output RiskDiffCol2=risk(where=(index(row,'Total')=0));
proc freq data=all;
  by _imputation_;
  tables trt01p*resp/riskdiff;
run;
proc sort data=risk; by row;
ods output VarianceInfo=Variance1;
ods output ParameterEstimates=Param1;
proc mianalyze data=risk;
  by row;
  modeleffects risk;
  stderr ase;
run;
```

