5.5. Other Effectiveness Endpoints Analysis

The other effectiveness endpoints listed in [Table 5-4](#) will be summarized descriptively based on the observed data.

The analyses of CP will be performed for the mITT population at Baseline and Month 1. The analyses of TP will be performed for the VT population at Baseline and Months 1, 2, 4, and 6.

JUVÉDERM VOLITE™ XC

The analyses of RP will be performed for the VRT population at Baseline and Months 1 and 4 post the repeat treatment.

The composite responder status is defined based on ACSS and FACE-Q Satisfaction with Skin Questionnaire overall converted score. A participant is counted as a composite responder if both criteria listed below are met:

- ACSS criterion: A participant with at least 1-point reduction from baseline in ACSS on both cheeks will be considered as an ACSS responder
- FACE-Q satisfaction with skin responder: A participant with change from baseline in FACE-Q overall converted score \geq half of standard deviation of FACE-Q overall converted score at baseline ([Pusic 2013](#))

Table 5-4 **Other Effectiveness Analyses**

Endpoint	Description	Analysis Period	Methodology
ACSS responder status as assessed by EI	Number (%) of responders by treatment group	TP, RP	Frequency counts and percentages
Raw value and change from baseline in ACSS	Summary by treatment group	CP, TP, RP	Continuous descriptive statistics
Raw value and change from baseline in FACE-Q Satisfaction with Skin questionnaire overall converted score	Summary by treatment group	TP, RP	Continuous descriptive statistics
Item score of FACE-Q Satisfaction with Skin questionnaire and aggregated categories of “satisfied” and “dissatisfied”	Number (%) of each response category by treatment for each of 12 individual items	CP, TP, RP	Frequency counts and percentages
AFLS responder status as assessed by EI	Number (%) of responders by treatment group	TP, RP	Frequency counts and percentages
Raw value and change from baseline in AFLS	Summary by treatment group	CP, TP, RP	Continuous descriptive statistics
Raw value and change from baseline in FACE-Q Appraisal of Lines questionnaire overall converted score (see Section 6.5.3 and Section 6.5.4)	Summary by treatment group	CP, TP, RP	Continuous descriptive statistics

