6.2. Appendix 2: Changes to SAP Version 1 Analyses

The following are changes to [version 1](#) of SAP:

1. The naming of the analysis population for the sensitivity analysis of primary endpoint, ACSS responder status at Month 1 was changed from “Completer Population” to “Observed Primary Endpoint” in Section 4. The definition of this population refers to the completion of the primary timepoint visit (ie., Month 1 of CP). This naming change is aimed to avoid potential confusion with study completion.
2. The wordings of “overall converted score” were specified for the analyses of FACE-Q Satisfaction with Skin, FACE-Q Appraisal of Lines, and FACE-Q Recovery Early Life Impact in Sections 4, 5.4, 5.5 and 5.6.5 to enhance clarity and consistency with Appendix 6.5.
3. The cut-off for the of FACE-Q Satisfaction with Skin as one of the definitions for Fitzpatrick Safety Cohort was changed from 39 for the overall raw score to 69 for the overall converted score in Table 4-1.
4. The definition of “baseline” for the effectiveness and safety variables in Section 5.1 was changed to “the last non-missing assessment prior to the latter of randomization or first treatment in the control period” due to possibility of participants who were mis-treated (ie., either randomized to Volite but was not treated or randomized to Control but received Volite)
5. The multiple imputation for the primary effectiveness analysis described in Section 5.3.2 was revised to (1) include the baseline ACSS score and age in the model based on the correlation with the primary endpoint to be imputed (ie., ACSS score at Month 1 of CP) and (2) number of imputed dataset is increased from 5 to 30 to reduce variability and increase the efficiency of estimates
6. The derivation for skin hydration and analyses of following variables were added to other effectiveness analyses in Section 5.5:
 - a. raw value and change from baseline in ACSS
 - b. raw value and change from baseline in AFLS
 - c. item scores and aggregated categories for FACE-Q Satisfaction with Skin
 - d. item scores and aggregated categories for FACE-Q Appraisal of Lines
7. The analysis of ISR in Section 5.6.3 was revised to include: (1) ISR by maximum severity for summaries up to 30 days and beyond 30 days after treatment, (2) analysis of “other symptoms” based on the coded terms assigned by the Medical Safety Physician

JUVÉDERM VOLITE™ XC

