6.4. Data Handling Convention

6.4.1. Analysis Window

6.4.1.1. Effectiveness

Table 6-2, [Table 6-3](#), and [Table 6-4](#) below present the timepoints assigned for analyses and the corresponding range of study days for all the scheduled and unscheduled visits with complete dates. If a scheduled visit with incomplete date is available with no other visits with complete date during the visit window, then the visit with incomplete date may be used for analysis and the nominal visit will be used as the visit window (eg, if the only assessment collected for Month 2 visit window is on a Month 2 eCRF with incomplete date, then those data will be used for the Month 2 assessments).

If multiple assessments were taken within an analysis window, the assessment obtained on the day closest to the target day will be used; in the case of a tie, the assessment obtained on the later day will be used in the analysis.

Analysis visit windows for effectiveness endpoints are defined as follows:

If analysis date \geq reference date, then

$$\text{Analysis day} = \text{analysis date} - \text{reference date} + 1$$

If analysis date $<$ reference date, then

$$\text{Analysis day} = \text{analysis date} - \text{reference date}$$

Table 6-2 **Effectiveness Analysis Visit Definitions for Treatment Group and Control Group during Treated Period**

Scheduled Visit for Effectiveness Measure	Target Day of the Visit	Analysis Visit Window
Screening ^a	N/A	Screening visit; no more than 30 days prior to randomization
Baseline	N/A	Randomization/Initial Treatment visit
Last Treatment ^b	Day 1 of Last Treatment	Day 1
Month 1	Day 31 Post Last Treatment	Day 2 to Day 46
Month 2	Day 61 Post Last Treatment	Day 47 to Day 91
Month 4	Day 121 Post Last Treatment	Day 92 to Day 151
Month 6	Day 181 Post Last Treatment	Day 152 to Repeat Treatment Date (if applicable) or Study Exit Date, whichever is earlier

^a Participants may have screening and randomization on the same day. In such cases, only randomization visit is relevant

^b The last treatment refers to the latter of initial treatment or touch-up treatment (if applicable)

Table 6-3 Effectiveness Analysis Visit Definitions for Control Group during Control Period

Scheduled Visit	Target Day of the Visit	Analysis Visit Window
Randomization Day	Day 1	N/A
Month 1	Day 31	Day 2 to Optional Treatment Date or Study Exit Date, whichever is earlier.

Table 6-4 Effectiveness Analysis Visit Definitions for Treatment Group during Repeat Treatment Period

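### The primary imputation model for ACSS uses only age and baseline, and ignores Month 2 and pre-touch-up Day 30 ratings of the same cheek in the VOLITE arm

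*SAP*

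**What the plan says.** **Imputation model.** SAP 5.3.2 states: "The missing data will be imputed by cheek side and treatment group using the Fully Conditional Specification (FCS) method". The regression formula has age and baseline ACSS as its only predictors, and the PROC MI code agrees ("var age acss0 acss1"). SAP Appendix 2 (6.2, item 5) records that the revision was made to "include the baseline ACSS score and age in the model based on the correlation with the primary endpoint to be imputed". No rating made after treatment enters the model.

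**Ratings that exist.** On touch-up, Protocol 7.2 says: "The TI will have access to the EI-rated ACSS scores to assist in making the determination of whether optimal correction has been achieved". A footnote to the schedule fixes the order at a treatment visit: "The treatment procedure is to be performed after all effectiveness assessments and 2D facial imaging". A Day 30 rating in a touched-up subject therefore precedes the touch-up injection. Protocol Table 2-4 lists the evaluator's ACSS at Touch-up Day 30 and at Month 2 for delayed treatment. The grid of Table 2-2 (treatment group) is not in the text available here, so the Day 30 rating in that arm is inferred from the passages above. For Month 2, SAP 5.5 states: "The analyses of TP will be performed for the VT population at Baseline and Months 1, 2, 4, and 6". SAP Table 6-2 gives the treatment group a Month 2 window.

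**Timing.** Without a touch-up there is no separate Day 30 value: "If no touch-up treatment is performed, Day 30 visit becomes Month 1 visit". With one, SAP Table 6-2 counts Month 1 from the touch-up, with a window of Day 2 to Day 46. The pre-touch-up rating falls on Day 1 and a rating on Day 47 is classed as Month 2. Neither can serve as Month 1, and neither informs its imputation.

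**The concern.** The stated reason for the two predictors is their correlation with Month 1 ACSS. By that criterion, the same scale scored on the same cheek a month earlier or later is an obvious candidate, and the SAP gives no reason for leaving it out.

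Two groups of VOLITE subjects are affected:

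- Touched-up subjects whose clock restarts, who have a further month in which to be lost, and whose Day 30 rating is then unused.
- Subjects who miss the Month 1 window but return, whose Month 2 rating is unused.

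Both are imputed as the average VOLITE subject of their age and baseline score. If loss is related to how well the cheek responded, missing at random given age and baseline fails, while the data that would make it more plausible are already held. At stake are the primary point estimate and its confidence interval.

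**Working it through.** **1. The plan's own figures.** Exact two-sided Fisher power for 112 versus 56 at 80% versus 40% is 99.91% (stated 99.9%). Attrition: 168/(1 - 0.20) = 210, split 140 and 70. Both reproduce.

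**2. Inputs for the bias.**
- Overall VOLITE response 80% (SAP 3).
- Touched-up share t: 23.7% of subjects or 17.6% of cheeks in V12-001 (Protocol 3.2). Of 140 subjects that is 33 or 25.
- Response after touch-up pT: assumed 50%, 60% or 84%.
- Missing Month 1: assumed 20% or 30% in touched-up subjects (mT), 10% in the others (mN).

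**3. Formula.** The others respond at pN = (0.80 - t·pT)/(1 - t). Imputing at the whole-arm observed rate returns that rate, so

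bias = [t(1-mT)pT + (1-t)(1-mN)pN] / [t(1-mT) + (1-t)(1-mN)] - 0.80.

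Example with t = 0.237, pT = 0.50, mT = 0.20: pN = 0.6815/0.763 = 0.893; (0.1896 × 0.50 + 0.6867 × 0.893)/0.8763 = 0.8081, a bias of +0.81 points.

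| t | pT | pN | Bias, 20% vs 10% missing | Bias, 30% vs 10% missing |
|---|---|---|---|---|
| 23.7% | 50% | 89.3% | +0.81 | +1.67 |
| 23.7% | 60% | 86.2% | +0.54 | +1.11 |
| 23.7% | 84% | 78.8% | -0.11 | -0.22 |
| 17.6% | 50% | 86.4% | +0.60 | +1.22 |
| 17.6% | 60% | 84.3% | +0.40 | +0.81 |
| 17.6% | 84% | 79.1% | -0.08 | -0.16 |

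With equal loss in the two groups this component is zero.

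**4. How well pT is known.** If V12-001's 96.2% Month 1 response and 23.7% touch-up share describe the same subjects, touched-up subjects responded at no less than (96.2 - 76.3)/23.7 = 84%. With the 89.4% reported for cheeks moderate or severe at baseline, the floor is (89.4 - 76.3)/23.7 = 55%, or (89.4 - 82.4)/17.6 = 40% on the cheek touch-up share. The documents do not settle the value.

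**5. An effect in the other direction.** Cheeks are imputed separately, but response needs both. For a subject missing both, the imputed rate is roughly the product of the cheek rates. If each cheek responds at 85% (assumed), 0.85² = 72%, against 80% for both cheeks. With 0.237 × 20% + 0.763 × 10% = 12.4% missing, the shift is 0.124 × (0.7225 - 0.80) = -0.96 points, enough to cancel the +0.81 above.

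**6. A harsher scenario.** A simulation of the VOLITE arm put all loss on touched-up subjects, 30% of Day 30 responders and 60% of Day 30 non-responders. Over four sets of assumed response rates, whole-arm imputation overstated the rate by 0.1 to 5.4 points. Conditioning on Day 30 status removed this, as expected when loss depends only on that status.

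**7. Splitting the whole arm by touch-up status.** A subject without touch-up who attends Day 30 already has Month 1. Those missing without a touch-up are therefore mostly lost before touch-up status is known. If 10% are lost early, unrelated to touch-up, and are coded as not touched up, they are imputed at pN. At t = 23.7% this adds 0.10 × (0.893 - 0.80) = +0.93 points (pT = 50%) or 0.10 × (0.862 - 0.80) = +0.62 (pT = 60%). In the 20% versus 10% case that is slightly worse than the SAP model's +0.81 and +0.54.

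**The case against.** **The choice is defensible and already bounded.** Appendix 2 explains why age and baseline were added; it does not claim that they are the best predictors. The tipping-point analysis in SAP 5.3.3 runs through every combination of missing subjects counted as responders. Even with 20% of the VOLITE arm missing and all counted as non-responders (0.80 × 0.80 = 64%, control left at 40%), Fisher power at 140 versus 70 is about 89%. This stands for the success decision. It does not improve the primary estimate or its interval, and the observed-case analysis ignores the same ratings.

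**Month 2 cannot help a subject who is lost for good.** Correct. It helps only those who miss Month 1 and return; for a touched-up subject lost before Month 1, only Day 30 is available.

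**Sparse data.** About 25 to 33 touched-up subjects, fewer after loss, must support a categorical model by cheek. This is a real cost. A gain in precision should not be claimed, because none has been shown for so small a group.

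**A stronger reading.** A reader might infer that the omission always inflates the VOLITE rate, because touch-up marks poor response. The documents do not support that. Touch-up follows the treating investigator's view that correction is not yet optimal, agreed with the subject. That is not ACSS non-response, and the touch-up may work. Steps 3 and 5 show that the sign can reverse.

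**Conclusion.** The point holds as a modest improvement to the primary analysis. The imputation model leaves out ratings of the same cheek on the same scale: Month 2, and very probably Day 30 before touch-up. Its missing-at-random assumption is weaker than it need be.

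The direction of bias is not determined. Its size is probably under about 2 points on the VOLITE rate, given 17.6% to 23.7% touched up, 50% to 84% response after touch-up and 10% to 30% missing. Larger values, up to about 5 points, need loss concentrated in touched-up subjects with poor Day 30 ratings, and nothing in the documents indicates that. Against a planned 40-point difference and 99.9% power, the success decision is unlikely to change. Sample size and design power are unaffected.

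**What to change.** Revise SAP 5.3.2 for the VOLITE arm only:

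- Add Month 2 ACSS of the same cheek as an auxiliary variable in the FCS model, entered as a numeric score if categories are sparse.
- For subjects who actually received a touch-up and then missed Month 1, impute from touched-up subjects using their Day 30 ACSS. Day 30 cannot simply join the variable list, because without a touch-up it is Month 1.
- Keep subjects lost before Day 30 in the whole-arm model. State that they are not to be coded as having had no touch-up.
- Prespecify the present age-plus-baseline model as the fallback if the extended model does not converge.

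Leave the control model unchanged: control subjects' Month 2 ratings follow delayed treatment.

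The cost is a few lines of text and code, with no new data. The downside is sparse imputation cells among about 25 to 33 touched-up subjects. If the sponsor prefers to keep the primary model, the same specification could be added to 5.3.3 as a third sensitivity analysis.

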5.3.3. Sensitivity Analyses

Two sensitivity analyses of the primary effectiveness endpoint, the ACSS responder status at Month 1 in CP based on EI's assessment, will be performed as follows:

- A tipping point analysis using the mITT population will be conducted to evaluate all possible combinations of participants with missing Month 1 ACSS assessments counted as responders in both treatment groups. A diagram of 2-sided p-values based on the Fisher's exact test with the x-axis and y-axis displaying the number of imputed responders out of the total number of participants with missing Month 1 ACSS assessment in VOLITE and Control group, respectively and the p-values ≤ 0.05 and >0.05 in different colors will be presented.
- The ACSS responder at Month 1 of CP will be analyzed using the Observed Primary Endpoint population. The number and proportion of participants of ACSS responder will be tabulated by treatment group. The between-group difference in the responder rate, 95% CI for the responder rate difference, and p-value based on the Fisher's exact test will be presented.

5.4. Secondary Effectiveness Endpoints Analysis

5.4.1. Secondary Effectiveness Endpoints

The secondary effectiveness endpoints are change from baseline in FACE-Q Satisfaction with Skin overall converted score at Month 1 during the CP and AFLS responder at Month 1 during the CP.

Each participant's responses to the 12 items on the FACE-Q Satisfaction with Skin questionnaire will be summed and converted to a scale score that ranges from 0 to 100 (higher score indicates more satisfaction) using the algorithm developed by the FACE-Q scale developers (see [Sections 6.5.1](#) and [6.5.2](#) for details of derivation). The mean change from baseline in FACE-Q overall converted score at Month 1 will be calculated. The change from baseline value will be computed as the value for the postbaseline visit minus the baseline value. The analysis will be conducted using observed data (eg, no imputation for missing baseline or Month 1 FACE-Q scale scores).

An AFLS responder is defined as participant who achieves at least 1-point improvement from baseline on the AFLS scale (see Table 5-3) on both cheeks.

Table 5-3 **Allergan Fine Lines Scale**

Score	Grade	Description
0	None	No fine lines
1	Minimal	1-2 superficial lines
2	Moderate	3-5 superficial lines
3	Severe	Greater than 5 superficial lines; no crosshatching
4	Diffuse	Diffuse superficial lines; crosshatching

